6.2.6 Missing Last Dates of Study Drug Dosing

If the date of last dose of study drug is completely missing, then the date of last dose of study drug will be taken for analysis purposes as the date when the patient would have run out of study drug assuming full compliance from the date the study drug was last dispensed, or the date of patient's last clinic visit in the study or early termination or death whichever the earlier.

If only the month and year of the last dose was recorded, then the date of last dosing will be taken for analysis purposes as the date the patient would have run out of study drug assuming full compliance from the date the study drug was last dispensed, the last day of the month of the recorded last dose or the date of patient's last clinic visit in the study or early termination or death whichever the earlier.

6.2.7 Inexact Values

In the case where a variable is recorded as "> x", " \ge x", "< x" or " \le x", a value of x will be taken for analysis purposes.

6.2.8 Electrocardiogram Data

For electrocardiogram (ECG) data recorded on continuous scales, if more than one value is recorded at a time point, the mean value (taken from the non-missing values) rounded to the integer will be presented. For overall interpretation, if more than one value is recorded, the most severe (worst case) of the respective readings will be taken.

QMD Ref: Worldwide-TMP-ST-005-7.0 Effective: 12Aug2019	Governing QMD: Worldwide-SOP-ST-001	
Confidentiality Statement		
This document is the property of Worldwide Clinical Trials Inc. and may not be duplicated, copied, altered or removed from company without prior approval from Worldwide Quality Assurance or in compliance with Worldwide Standard Operating Procedures.		
REF: Worldwide-TMP-QA-001f-1.3	Page 16 of 49	

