11.1.6. Resting 12-lead ECG

12-lead ECGs will be recorded in a supine position after five minutes of rest. PR, QRS, QT, and QTcF intervals will be recorded. Three ECGs will be recorded at screening visit, separated by at least one minute. Single ECG for all other visits. The time of the ECG recordings must be noted in the CRF.

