6.2.2 Baseline

Baseline is defined as the last non-missing value (either scheduled, unscheduled or repeat) before the patient receives the first dose of study drug.

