6.17.4 Electrocardiogram Data

Descriptive statistics for observed values and changes from baseline in the following ECG variables will be presented by treatment group and visit:

- Heart rate (bpm)
- PR interval (ms)
- QRS duration (ms)
- OT interval (ms)
- QTc interval (ms)
- QTcB interval (ms) [Bazett's formula]
- QTcF interval (ms) [Fridericia's formula]
- RR interval (ms) •

Shift tables in relation to the overall interpretation i.e., Normal, Abnormal NCS (Not Clinically Significant), and Abnormal CS (Clinically Significant) from baseline to each follow-up visit will be presented.

Any QTcF or QTcB Interval (ms) result meeting the following criteria will be identified as an electrocardiogram abnormality and a separate tabulation by treatment group will be provided:

- Interval at Baseline of >450 msec and \leq 480 msec
- Interval at Baseline of >480 msec and \leq 500 msec
- Interval at Baseline of >500 msec
- Post-Baseline value of >450 msec and < 480 msec
- Post-Baseline value of >480 msec and \leq 500 msec
- Post-Baseline value of >500 msec
- Post-Baseline increase of >30 msec and < 60 msec
- Post-Baseline increase of >60 msec

All ECG data, including details of any abnormalities, will be listed.

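### For patients whose baseline ECG is the screening triplicate, the overall-interpretation shift table sets a worst-of-three baseline against single later readings, so it under-counts Normal-to-Abnormal shifts.

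*SAP*

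**What the plan says.** **Number of readings.** Protocol section 11.1.6: "Three ECGs will be recorded at screening visit, separated by at least one minute. Single ECG for all other visits". The schedule of procedures and section 10.4 add a single Visit 1 ECG only when 29 days or more separate screening from Visit 1. Screening may fall anywhere from Day -56 to Day -10.

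**Combining readings.** SAP section 6.2.8 has two rules. For continuous ECG variables, "the mean value (taken from the non-missing values) rounded to the integer will be presented". For the Normal / Abnormal NCS / Abnormal CS call, "For overall interpretation, if more than one value is recorded, the most severe (worst case) of the respective readings will be taken".

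**Baseline.** SAP section 6.2.2: "Baseline is defined as the last non-missing value (either scheduled, unscheduled or repeat) before the patient receives the first dose of study drug".

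**Tables.** SAP section 6.2.11 keeps post-baseline repeat and unscheduled assessments out of the tabulations. SAP section 6.17.4 plans shift tables of the overall interpretation from baseline to each follow-up visit. It also plans categorical tables of QTcF and QTcB. Two of their bins are printed as "Post-Baseline value of >450 msec and < 480 msec" and "Post-Baseline increase of >30 msec and < 60 msec", and the next bins up start above 480 and above 60. The corresponding baseline bin runs to 480 inclusive.

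**The concern.** A worst-case rule is cautious when it acts after dosing. At baseline it works the other way, because it makes the patient look worse before treatment. A patient with one abnormal reading in three starts the shift table as abnormal, and a later abnormal reading of the same category then shows no shift. A later normal reading shows as an improvement that no treatment produced.

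Safety is summarised descriptively and no DSMB analysis is planned, so this table is one of the main places where a reader will look for new ECG abnormalities. The two unbinned QTc values are a separate and smaller matter: a result that falls exactly on the boundary would be missing from the table.

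**Working it through.** The documents state no ECG rate or count, so there is no plan figure to reproduce. All rates below are assumptions.

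**1. Where the rule acts**

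| Gap from screening to Visit 1 | Baseline ECG | Baseline interpretation | Each later visit |
|---|---|---|---|
| 28 days or less | screening triplicate | worst of 3 | 1 reading |
| 29 days or more | single Visit 1 ECG | 1 reading | 1 reading |

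This assumes no unscheduled ECG between screening and first dose. Only the first row is asymmetric. The documents do not give its share of patients; call it w.

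**2. Share labelled abnormal at a triplicate baseline**

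Let p be the chance that a single reading is abnormal and ρ the intraclass agreement. In a beta-binomial model, m = (1 − ρ)/ρ, a = pm and b = (1 − p)m.

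- P(all three normal) = b(b+1)(b+2) / [m(m+1)(m+2)]
- Worst-of-three abnormal share = 1 − P(all three normal)

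Low end, p = 0.20 and ρ = 0.8: m = 0.25, b = 0.20. P(all normal) = 0.2 × 1.2 × 2.2 / (0.25 × 1.25 × 2.25) = 0.528/0.703 = 0.751. Abnormal share 24.9%.

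High end, p = 0.30 and ρ = 0.6: m = 0.667, b = 0.467. P(all normal) = 1.688/2.963 = 0.570. Abnormal share 43.0%.

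**3. Effect on shifts with no drug effect**

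Here the later reading is assumed to agree with baseline as closely as the replicates agree with each other.

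- Normal to Abnormal, single baseline: ab / [m(m+1)]
- Normal to Abnormal, worst of three: ab(b+1)(b+2) / [m(m+1)(m+2)(m+3)]
- Net apparent improvement = worst-of-three share − p

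| p | ρ | Baseline abnormal, worst of 3 | Net apparent improvement | N→A, single baseline | N→A, worst of 3 | Ratio |
|---|---|---|---|---|---|---|
| 0.20 | 0.8 | 24.9% | 4.9 points | 3.2% | 1.2% | 0.36 |
| 0.20 | 0.6 | 30.1% | 10.1 points | 6.4% | 2.5% | 0.40 |
| 0.30 | 0.8 | 36.4% | 6.4 points | 4.2% | 1.5% | 0.35 |
| 0.30 | 0.6 | 43.0% | 13.0 points | 8.4% | 3.1% | 0.37 |

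The loss is smaller when readings agree less. With independent readings and p = 0.10, the Normal-to-Abnormal share is p(1−p)³ = 7.3% against p(1−p) = 9.0%, a ratio of 0.81. The direction does not change.

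These figures apply to triplicate-baseline patients. Over the whole study the net improvement is multiplied by w: at w = 0.5, for example, 4.9 to 13.0 points becomes about 2.5 to 6.5.

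**4. Does the middle category remove it?**

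P(at least two of three abnormal) = [3a(a+1)b + a(a+1)(a+2)] / [m(m+1)(m+2)]. For p = 0.20 this is 19.8% (ρ = 0.8) or 19.0% (ρ = 0.6). For p = 0.30 it is 29.8% or 29.2%. The baseline share therefore stays within about 1 point of the single-reading share. One prespecified reading matches it exactly.

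**5. QTc bins**

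Checking every integer against the printed bins, the only post-baseline value above 450 left out is 480, and the only increase above 30 left out is 60. The baseline bins have no gap. Under an assumed mean of 420 to 430 ms and SD of 20 to 25 ms, P(exactly 480) is 0.02% to 0.22% per reading. At the upper end this is Φ(50.5/25) − Φ(49.5/25) = 0.9783 − 0.9761 = 0.0022. For +60, with mean change 0 to 10 ms and SD 15 to 25 ms, it is about 0.001% to 0.22%.

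**The case against.** The case for leaving the plan alone has real force, and most of it limits the scope of the point.

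- **One table only.** A reader might infer that all the ECG tables use a worst-of-three baseline. They do not: section 6.2.8 averages continuous values, so the interval and QTc tables are outside this point.
- **Not every patient.** Anyone screened 29 days or more before Visit 1 has one reading on each side of the comparison.
- **Clinically significant findings.** A reader might infer that these are hidden. Exclusion criterion 10 bars clinically significant abnormal ECGs at entry, so a worst screening reading should be Abnormal NCS at most. A new Abnormal CS reading would still show as a shift, and all ECG data and abnormalities are listed.
- **Same rule in all arms.** A reader might infer a bias in favour of mesdopetam. The documents do not support that. Counts are attenuated in every arm, which can dilute a difference but does not create one.
- **QTc change.** A reader might also infer that the two baseline types hide QTc increases. With an assumed between-day SD of 8 ms and replicate SD of 6 ms, the change variance is 100 + 100 = 200 for a single baseline and (64 + 36/3) + 100 = 176 for a triplicate mean. The false rate above 30 ms is then about 1.7% against 1.2%. The difference is small, and it adds flags in the single-baseline patients.
- **Bins.** Neighbouring bins carry a less-than-or-equal sign, so an underline may have been lost in the PDF text. Values above 480, above 500 and above +60 are counted either way.

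One could also argue that section 6.2.2, read literally, makes the third reading of the triplicate the baseline. The SAP does not say whether 6.2.2 or 6.2.8 governs a triplicate. That is a further reason to state the rule.

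None of this removes the asymmetry in the one table, for the patients whom it affects.

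**Conclusion.** The point holds in a limited form and is minor. When a screening triplicate is the baseline, the overall-interpretation shift table under-counts Normal-to-Abnormal shifts, mainly Normal to Abnormal NCS, and shows improvement that is not there. Under the assumed 20 to 30% abnormal rate and agreement of 0.6 to 0.8, the rule adds about 5 to 13 points to the baseline abnormal share in those patients and cuts the no-effect Normal-to-Abnormal share to 0.35 to 0.40 of its single-baseline value. Those sizes rest wholly on assumed rates; the direction does not. The study-wide effect also depends on the unknown share of patients with a triplicate baseline.

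The bin gap is real as printed but very small, and it has to be confirmed on the original SAP page before it is called an error.

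**What to change.** In SAP section 6.2.8, state that the baseline overall interpretation from a triplicate is the middle (majority) category of the three readings, or one prespecified reading, and that this governs over the general baseline wording in section 6.2.2. Keep worst case only for post-baseline replicates. The averaging of continuous intervals and the choice of the last pre-dose ECG as baseline can stay as they are.

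In SAP section 6.17.4, check the two signs on the original page. If they are as printed, change the bins to >450 to ≤480 ms and >30 to ≤60 ms, so that 480 ms is counted as it is at baseline and +60 ms is also counted.

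The cost is SAP wording and derivation code. No new data are needed.

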6.2.9 Vital Signs

For blood pressure and pulse rate, the orthostatic changes will be calculated as standing minus supine readings. Patients meeting the following criteria will be identified:

- Patients with > 20 mmHg reduction (standing minus supine) in systolic blood pressure at 1 minute or 3 minutes of standing.
- Patients with > 10 mmHg reduction (standing minus supine) in diastolic blood pressure at 1 minute or 3 minutes of standing.

6.2.10 Columbia-Suicide Severity Rating Scale (C-SSRS)

The following outcomes are C-SSRS categories and have binary responses (yes / no). The categories have been re-ordered from the actual scale to facilitate the definition of composite endpoints:

Wish to be Dead
Non-specific Active Suicidal Thoughts
Active Suicidal Ideation with Any Methods (Not Plan) without Intent to Act
Active Suicidal Ideation with Some Intent to Act, without Specific Plan
Active Suicidal Ideation with Specific Plan and Intent
Preparatory Acts or Behaviour
Aborted Attempt
Interrupted Attempt
Actual Attempt (non-fatal)
Completed Suicide

Suicidal Ideation since baseline – A "yes" answer at any time during double blind treatment to any one of the 5 suicidal ideation questions (categories 1-5) on the C-SSRS.

Suicidal Behaviour since baseline -A "yes" answer at any time during double blind treatment to any one of the 5 suicidal behaviour questions (categories 6-10) on the C-SSRS.

There will be no imputation of missing data for C-SSRS.

QMD Ref: Worldwide-TMP-ST-005-7.0 Effective: 12Aug2019	Governing QMD: Worldwide-SOP-ST-001	
Confidentiality Statement		
This document is the property of Worldwide Clinical Trials Inc. and may not be duplicated, copied, altered or removed from company without prior approval from Worldwide Quality Assurance or in compliance with Worldwide Standard Operating Procedures.		
REF: Worldwide-TMP-QA-001f-1.3	Page 17 of 49	

Worldwide Clinical Trials Controlled Quality Management Document		
WORLDWIDE CLINICAL TRIALS	Sponsor:	Integrative Research Laboratories Sweden AB
	Protocol Number:	IRL790C005
STATISTICAL ANALYSIS PLAN. PHASE 2-3-4		

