11.2.2. Columbia Suicide Severity Rating Scale (C-SSRS)

Suicidality will be assessed by trained study personnel using the C-SSRS [9]. The C-SSRS is a standardized suicidality rating system conducted by a certified rater. The interview measures presence of suicidality and consists of 4 categories: suicidal ideation, intensity of ideation, suicidal behaviour, and actual/potential lethality. This scale will be used for baseline as well as to assess for the occurrence of any suicidal ideation and/or behaviour during the study.

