6.17.6 C-SSRS

C-SSRS outcomes (Suicidal Ideation and Suicidal Behaviour) since baseline will be tabulated by treatment group and overall, by visit. A shift table for the change in number and percent of patients in each category (No Suicidal Ideation or Behaviour, Suicidal Ideation, Suicidal Behaviour) from baseline to each visit will be presented. Patients with both Suicidal Ideation and Suicidal Behaviour will be included in the Suicidal Behaviour category.

All reported data will be listed.

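### The planned C-SSRS tables do not register worsening within the ideation class or within the behaviour class; one added descriptive table from data already collected would show it

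*SAP*

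**What the plan says.** SAP 6.2.10 introduces ten items: "The following outcomes are C-SSRS categories and have binary responses (yes / no". Categories 1 to 5 are ideation, running from "Wish to be Dead" to "Active Suicidal Ideation with Specific Plan and Intent". Categories 6 to 10 are behaviour. The SAP says it changed the scale's own order so that composites could be defined.

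Two outcomes are derived. Ideation since baseline is a yes answer "at any time during double blind treatment to any one of the 5 suicidal ideation questions (categories 1-5) on the C-SSRS". Behaviour since baseline is a yes, at any time on treatment, to "any one of the 5 suicidal behaviour questions (categories 6-10) on the C-SSRS". Missing C-SSRS data are not imputed.

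SAP 6.17.6 plans two tables:

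- "C-SSRS outcomes (Suicidal Ideation and Suicidal Behaviour) since baseline will be tabulated by treatment group and overall, by visit".
- A shift table whose classes are listed as "No Suicidal Ideation or Behaviour, Suicidal Ideation, Suicidal Behaviour) from baseline to each visit will be presented". A patient with both ideation and behaviour goes into the behaviour class.

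Everything else goes to listings. Protocol 11.2.2 says the interview "consists of 4 categories: suicidal ideation, intensity of ideation, suicidal behaviour, and actual/potential lethality"; the SAP defines no summary of intensity or lethality. Protocol 14.10 promises data summaries for safety, without formal analysis, and asks for no finer C-SSRS table.

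**The concern.** The C-SSRS is a named safety endpoint (Protocol 5.2, SAP 3.6), reported under the frequency and nature of findings. Two any-yes composites give frequency but little about nature. The five ideation items describe plainly different states, and the planned tables treat them as one.

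The SAP is finer with other graded safety data. MDS-UPDRS Question 1.6, also a safety endpoint, gets a shift table over every score from 0 to 4 and a count of patients who worsen by at least 2 points (SAP 6.17.7). Adverse events are tabulated by maximum grade (SAP 6.17.1), and QTc by threshold and size of increase (SAP 6.17.4). The C-SSRS has neither a level-by-level shift nor a worsening count, and no reason is given.

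At stake is whether the report shows by-dose counts of worsening suicidality for a CNS-active drug in a population that may include patients with controlled mild depression (exclusion criterion 12). No estimate or test depends on it.

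**Working it through.** The plan gives no figure to reproduce. The check traces example patients through the planned tables.

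**Inputs.** Ideation levels 1-5 and behaviour categories 6-10 are numbered as in SAP 6.2.10, with 0 for none. The shift classes and the rule that behaviour takes precedence come from SAP 6.17.6. The C-SSRS is rated at baseline (Visit 1) and on treatment at Visits 3, 4 and 5 (protocol schedule of procedures).

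**Tracing patients.** Each entry is the highest-numbered category answered yes.

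| Patient | Baseline | Visits 3, 4, 5 | Ideation composite | Behaviour composite | Shift at Visit 5 |
|---|---|---|---|---|---|
| A | 1 | 1, 1, 1 | yes | no | ideation to ideation |
| B | 1 | 1, 5, 5 | yes | no | ideation to ideation |
| C | 0 | 1, 1, 1 | yes | no | none to ideation |
| D | 0 | 1, 5, 5 | yes | no | none to ideation |
| E | 5 | 5, 6, 6 | yes | yes | ideation to behaviour |

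1. A and B agree in every cell at every visit, although B has moved from level 1 to level 5.
2. C and D also agree throughout, so the severity of new ideation is not shown either.
3. A and C have the same ideation composite, although A's ideation is unchanged and C's is new. The shift table does separate these two.
4. E is visible, because the move crosses a class boundary.
5. The same reasoning applies within behaviour. A patient with category 6 at baseline is classed behaviour to behaviour whether the on-treatment answer is category 6 again or category 9.

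**Counting moves from an ideation start.** Upward moves within ideation: C(5,2) = 5 × 4 / 2 = 10, none visible. Moves from an ideation level to a behaviour category: 5 × 5 = 25, all visible. Total 10 + 25 = 35, of which 25 / 35 = 71% are visible. These are possible moves, not patients.

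**General conventions.** SAP 6.3.4 shows all categories of a variable, and SAP 6.3.6 summarises all observed data unless otherwise specified. Neither closes the gap, because SAP 6.17.6 specifies which categories are used.

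**The case against.** The strongest reply is that the gap is small and presentational. Item-level answers are listed, and SAP 6.3.6 sorts listings by treatment group, patient and visit. With 154 patients over four arms (154 / 4 = 38.5 per arm) and few expected positives, a reader could follow each case. Exclusion criterion 12 bars a history of major depression or psychosis, so few patients should start in either class, least of all behaviour. SAP section 6 allows extra tables in the report if the data warrant them. No protocol commitment is broken, including for intensity and lethality. All of this stands and keeps the severity low. It does not remove the point, because listings give no by-arm counts and a prespecified table is better than one chosen after the data are seen.

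Four stronger readings are tempting, and the documents do not support them:

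- A reader might infer that the tables cannot show any worsening in patients who start with ideation. The shift table shows every move from ideation to behaviour.
- A reader might infer that no planned table of any kind would change. The adverse event tables in SAP 6.17.1 could change if the investigator reports the worsening as an adverse event, though nothing makes a C-SSRS rating one automatically. A completed suicide would appear among deaths.
- A reader might take the share of hidden level pairs across all ten items as the size of the problem. That treats abstract pairs as equally likely and says nothing about patients.
- A reader might infer that the SAP ranks all ten items by severity. It re-ordered them to form composites and states no ranking. The ideation gradient is clear from the item wording; the behaviour order is less explicit.

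**Conclusion.** The point holds for the two C-SSRS tables. Worsening within ideation or within behaviour changes no cell, and the ideation composite does not separate new from unchanged ideation. The number of patients affected cannot be derived from the documents and is probably small. No efficacy result, test or endpoint definition changes.

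The conclusion rests on reading SAP 6.17.6 as the full list of C-SSRS tables. The table shells are not in the text available, so their rows could not be checked. It also assumes that the five ideation items are ordered as their wording indicates. The absence of DSMB analyses adds little, because end-of-study tables give no ongoing oversight with or without extra rows. This is a low-severity improvement that costs almost nothing.

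**What to change.** In SAP 6.2.10 and 6.17.6, keep the two composites and the three-class shift, and add one descriptive table by treatment arm with:

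1. The number of patients with a yes to each of the ten categories, at baseline and at any time on treatment.
2. The number and percent with new or worsened ideation. Let B be the highest ideation level (0 for none, otherwise 1-5) at baseline and W the highest on treatment; count the patient if W > B. In the example, B, C and D count and A does not; the rows in item 1 then separate C from D.
3. The number and percent with new behaviour, meaning a yes on treatment to any behaviour category not present at baseline. This needs no ranking of the behaviour items.

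State in the SAP that ideation items 1-5 are treated as ordered, and do not use a single 0-10 scale across ideation and behaviour. For items 2 and 3, take as denominator the patients with a baseline and at least one on-treatment C-SSRS, without imputation, in line with SAP 6.2.10.

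The cost is one added table and a few lines of SAP text, from data already collected.

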6.2.11 Unscheduled Visits

Only scheduled post-baseline assessments will be summarized and tabulated. Post-baseline repeat or unscheduled assessments will not be tabulated but will be included in listings of individual patient data.

6.2.12 24-Hour Patient Home Diary

Patients will complete the 24-hour home diary on 3 separate days during the week preceding a visit. Patients will record their motor function in 30-minute intervals over 24-hours, beginning at midnight. For each 30-minute interval, the patient will rate the motor state he or she has been in for the past 30 minutes. Diary data will then be transcribed to the CRF by the clinic staff (ON without troublesome dyskinesia, ON with troublesome dyskinesia, OFF, Asleep, Missing entry, Invalid entry).

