During the treatment period at Visits 3-5, changes in disease state and ON-phase dyskinesia will be assessed using the MDS-UPDRS, the modified UDysRS (i.e. parts 1, 3 and 4) standardized for levodopa intake and time of the day and Clinician's Global Impression of Severity (CGI-S). The MDS-UPDRS part 2 will be assessed at all clinical visits. Part 3 will be assessed with the patient in ON at Visit 1 and Visits 4 and 5.

Furthermore, patients will self-administer three 24-hour home diaries prior to Visit 3 (Week 4), Visit 4 (Week 8) and Visit 5 (Week 12) to assess daily motor function. Dates for the patient to complete home diaries will be agreed in advance. The clinic will call the patient the working day before the first scheduled 24-hour home diary completion period, as a reminder, and the working day after the last 24-hour home diary completion period to encourage compliance. Patients must bring all three diaries to the clinic at each visit.

At Visit 4 and Visit 5, the morning IMP dose will be administered at the clinic. Blood samples for PK analysis will be collected within 15 min pre-dose and approximately two hours $(\pm 15 \text{ min})$ post dose.

Various parts of the safety assessments will be performed at all visits. The morning dose at Day 84 (Visit 5, EOT) will be the last dose of IMP.

Visit 6 (follow-up) will be performed for all patients, including any patients that discontinue the IMP early, 5-8 days after last administration of IMP.

Unscheduled visits will be performed as needed during the study and should be documented in the appropriate section of the Case report form (CRF).

Each assessment is further described in Section 10.

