10.10. Visit 4 (Day 56 ± 4 days)

The following procedures and assessments are to be carried out at Visit 4:

- Concomitant Medications
- Vital signs (including supine/standing BP)
- 12-lead ECG
- Haematology/ Serum Chemistry (prolactin should not be included) /Coagulation
- CYP2D6 genetic testing. Note: A genetic ICF must be signed prior testing.
- Dipstick Urinalysis
- Urine pregnancy test (if applicable)
- MDS-UPDRS (all parts)
- Modified UDysRS (part 1, 3 and 4)
- Three 24-hour patient home diaries collected
- Three empty 24-hour patient home diaries handed out
- CGI-S
- C-SSRS
- PK sample 15 min pre-dose and approximately two hours (± 15 min) post dose. Patient need to bring the IMP morning dose to the site.
- AEs/SAEs
- Collect empty bottle of IMP
- IMP compliance

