6.17.3 Vital Signs

Descriptive statistics for observed values and changes from baseline in the following vital signs will be presented by treatment group and visit:

- Systolic blood pressure (mmHg)
- Diastolic blood pressure (mmHg)
- Pulse rate (bpm)
- Body weight (kg)

Both standing and supine values, as well as orthostatic changes (standing – supine) will be presented for blood pressure and pulse rate. Measurements taken either seated or prone will be considered taken supine. The number and percentage of patients with either >20 mmHg reduction in systolic blood pressure after standing, or >10 mmHg reduction in diastolic blood pressure after standing, or both will be summarized. All vital sign data will be listed.

QMD Ref: Worldwide-TMP-ST-005-7.0 Effective: 12Aug2019	Governing QMD: Worldwide-SOP-ST-001	
Confidentiality Statement		
This document is the property of Worldwide Clinical Trials Inc. and may not be duplicated, copied, altered or removed from company without prior approval from Worldwide Quality Assurance or in compliance with Worldwide Standard Operating Procedures.		
REF: Worldwide-TMP-QA-001f-1.3	Page 44 of 49	

Worldwide Clinical Trials Controlled Quality Management Document		
WORLDWIDE CLINICAL TRIALS	Sponsor:	Integrative Research Laboratories Sweden AB
	Protocol Number:	IRL790C005
STATISTICAL ANALYSIS PLAN. PHASE 2-3-4		

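### SAP 6.2.11 keeps unscheduled and repeat results out of all tables without exempting the threshold counts, so the orthostatic count omits them and the QTc outlier table is in conflict with the rule.

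*SAP*

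**What the plan says.** The general rule is in SAP 6.2.11: "Only scheduled post-baseline assessments will be summarized and tabulated". The next sentence closes off the alternative: "Post-baseline repeat or unscheduled assessments will not be tabulated but will be included in listings of individual patient data". Neither sentence exempts any safety table.

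Two safety displays count threshold crossings rather than describe a visit:

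- **Orthostatic drop.** SAP 6.2.9 defines the criteria (a standing-minus-supine fall of more than 20 mmHg systolic or more than 10 mmHg diastolic, at 1 or 3 minutes). SAP 6.17.3 then summarizes "The number and percentage of patients with either >20 mmHg reduction in systolic blood pressure after standing", or the diastolic equivalent, or both.
- **QTc outliers.** SAP 6.17.4 says "Any QTcF or QTcB Interval (ms) result meeting the following criteria will be identified as an electrocardiogram abnormality", with a separate tabulation by treatment group. The post-baseline categories (above 450, 480 and 500 msec, and increases above 30 and 60 msec) are not tied to a visit.

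The protocol expects assessments outside the schedule. Section 6.1 says "Unscheduled visits will be performed as needed during the study".

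**The concern.** By-visit means and shifts need a fixed set of visits, and SAP 6.2.11 protects that. A count of patients who crossed a safety threshold asks something else: whether it happened at any point after baseline. Unscheduled and repeat readings are often taken because of a symptom or an earlier abnormal value, so they are more likely than routine readings to show a crossing. A rule that removes them can only lower the count.

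The stakes are in the safety description. Protocol 14.10 plans data summaries only, with no formal safety testing, and SAP section 8 plans no DSMB analyses. The by-arm threshold counts are therefore a visible part of how the dose groups will be compared on QTc and blood pressure. If the text can be read two ways, two programmers can also produce different QTc tables from the same data.

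**Working it through.** The plan states no figure on this point, so there is none to reproduce. The check compares the texts and then looks at the visit schedule.

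**1. Does anything override SAP 6.2.11?**

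- *Orthostatic count (6.2.9, 6.17.3).* Neither section mentions unscheduled or repeat readings or uses any-time wording. The general rule applies, and falls seen at unscheduled visits are not counted.
- *QTc table (6.17.4).* It refers to any QTcF or QTcB result but does not name unscheduled or repeat ones. SAP 6.3.6 limits summaries to scheduled visits but allows exceptions specified elsewhere. One reader can take 6.17.4 as such an exception. Another can apply 6.2.11 literally. The text does not decide between them.
- *Baseline (6.2.2), for contrast.* Scheduled, unscheduled and repeat values are all accepted before the first dose, so the two sides of the comparison follow different rules.

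**2. What does the schedule leave to unscheduled readings?** Inputs are Protocol 10.8, 10.10, 10.12, 10.13 and 11.1.6, and the 84-day treatment period.

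- *ECG.* For a patient who stays on treatment, post-baseline ECGs fall at Visits 4, 5 and 6. The rule for every visit after screening is "Single ECG for all other visits". With Visit 4 on Day 56, the days before it are 55 / 84 = 65% of treatment. The ± 4-day window gives 51 / 84 = 61% to 59 / 84 = 70%.
- *Supine/standing blood pressure.* The first post-baseline reading is Visit 3. With Day 28, 27 / 84 = 32%. The ± 4-day window gives 23 / 84 = 27% to 31 / 84 = 37%.
- *Early discontinuers.* They should, if possible, have Visit 6 assessments 5 to 8 days after the last dose (Protocol 7.4, 10.13, 10.14), including ECG and vital signs. SAP 6.2.3 tabulates early-withdrawal assessments as a separate visit, with windows that begin in the run-in. These patients can therefore have a tabulated ECG well before Week 8. Protocol 4.6 gives a plasma half-life of around 7 hours, so 5 days is 120 / 7 = about 17 half-lives. That ECG describes the patient essentially off drug.

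**3. How much does one omitted patient matter?** SAP section 4 gives 154 randomized. Assuming equal arms with everyone dosed, 154 / 4 = 38.5 per arm.

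- One patient in one arm: 1 / 38.5 = 2.6 percentage points.
- One patient in the pooled active arms: 1 / (3 × 38.5) = 1 / 115.5 = 0.9 percentage points.
- With 140 randomized (35 per arm): 1 / 35 = 2.9 percentage points.

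**4. Does admitting repeats settle the QTc table?** Not alone. SAP 6.2.8 averages continuous ECG values recorded at one time point and takes the worst case only for the overall interpretation. As an illustration with assumed values, 505, 490 and 490 msec average (505 + 490 + 490) / 3 = 495 msec. The patient would leave the category above 500 although one reading exceeded it.

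**The case against.** The case against is substantial, and most of it limits the point rather than removing it.

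- **No data are lost.** Every unscheduled result is listed. That stands, but a listing is not a by-arm count against fixed thresholds.
- **Important findings have another route.** Protocol 12.8 requires AEs, including clinically significant out-of-range laboratory values, to be recorded, and SAP 6.17.1 tabulates events from first dose to last follow-up. SAP 6.17.2 adds a listing of clinically significant laboratory measurements. A reader might infer that the rule understates safety reporting as a whole; the documents do not support that. The gap is in the threshold counts.
- **The QTc table may already be an exception.** The any-result wording, read with SAP 6.3.6, makes that reasonable. A reader might infer that an unscheduled QTc above 500 msec would certainly appear only in a listing, but the text leaves this open. What stands is a conflict between two sections.
- **Scheduled data exist before Week 8.** A reader might infer that no QTc or laboratory abnormality in the first 8 weeks could reach a table except through an unscheduled test. SAP 6.2.3 and Protocol 10.13 contradict that for early discontinuers. The long interval without a scheduled ECG applies to patients who stay on treatment.
- **Laboratory shift tables are not at fault.** They run from baseline to each follow-up visit, so an unscheduled value has no row in them. The SAP plans no worst-value laboratory table, and adding one would be a new analysis.
- **No size is shown.** The documents give no expected number of unscheduled ECGs or blood pressure readings. This stands in full.

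**Conclusion.** The point holds for the two threshold displays. As written, the orthostatic-drop count omits falls recorded at unscheduled visits. The QTcF/QTcB outlier table may or may not omit unscheduled ECGs, because SAP 6.2.11 and 6.17.4 disagree.

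For patients who stay on treatment, roughly the first 65% of the treatment period has no scheduled ECG and roughly the first 32% no scheduled orthostatic reading. In those stretches only unscheduled readings can show a crossing. Each patient left out changes an arm's rate by about 2.6 percentage points, assuming 154 patients split equally and all dosed. The number left out cannot be derived and could be zero. This is an inexpensive correction to a stated rule; the documents do not show that any safety conclusion would change.

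**What to change.** Amend SAP 6.2.11 to keep by-visit descriptive statistics and by-visit shift tables, including laboratory, on scheduled assessments. Then state that the QTc outlier table and the orthostatic-drop patient count use all post-baseline results, including unscheduled and repeat ones. Cross-refer to this in 6.17.3 and 6.17.4, and say in 6.17.3 that the orthostatic count is over the whole post-baseline period, since the section does not say whether it is by visit. State whether the averaging rule in 6.2.8 applies to the QTc outlier table.

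The cost is a few sentences of SAP text and a minor programming change. There is one real downside: patients with more unscheduled tests have more chances to be counted, so testing that differs between arms can itself shift the rates. Flagging counts that rest only on an unscheduled or repeat reading would let the reader see this.
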